## 10. Study Workflow and Procedures

1. **Screening and baseline:** Eligibility, informed consent, demographics and anthropometry (SECA stadiometer; Toledo 2096 PP scale;  $\text{BMI}=\text{kg}/\text{m}^2$  [27]). MEQ, PSQI, POMS administered once at baseline [20–22,28].
2. **Pre-session standards:** 24 h no heavy training; 24 h no alcohol; 6 h no caffeine; verbal verification at arrival [9,11,29].
3. **Nap session:** 13:50 adaptation; 14:00 N0/N25/N45; dark quiet room  $\approx 22^\circ\text{C}$ ; subjective verification [5,6]; prohibition of visual/stimulating activities [12,13].
4. **Warm-up:** Light jog plus 3-min mobility; heart rate monitored with Polar H10 for standardization [7].
5. **Performance tests:** 60 min post-awakening [2,3], Pro Agility  $\rightarrow$  3-min rest  $\rightarrow$  RSA (6×30 m, 20-s intervals [15–17]); RPE after each sprint [18].
6. **Post-session:** Hooper and VAS forms [8,19].

## 11. Data Collection Instruments and Quality Assurance

- **Devices:** SECA® stadiometer; Toledo 2096 PP scale; 16x Polar H10.
- **Validity/reliability:** MEQ, PSQI, POMS are validated instruments [20–22,28]; SmarTracks offers high temporal resolution; literature supports actigraphy-based sleep–wake verification with Fitbit [5,6].
- **Staff training:** Test administrators trained before data collection; measurement repeatability monitored.

## 12. Data Management

- **Coding and de-identification:** Participant IDs (e.g., P001–P016); personal data stored separately and encrypted.
- **Entry and verification:** Electronic CRFs; double checks and random source data verification.
- **Missing data:** Multiple imputation may be applied when appropriate; sensitivity analyses reported.
- **Access and retention:** Restricted to authorized researchers; retention per regulations.

## 13. Statistical Analysis Plan

- **Software:** SPSS v29.
- **Descriptives:** Mean $\pm$ SD, min–max.
- **Assumption checks:** Normality (skewness/kurtosis within  $\pm 1.5$ ), homogeneity (Levene), sphericity (Mauchly; Greenhouse–Geisser corrections if violated).
- **Primary analysis:** RM-ANOVA across N0–N25–N45; Bonferroni where appropriate.
- **Effect sizes:**  $\eta^2$  (small  $<0.06$ ; medium  $0.06–<0.14$ ; large  $\geq 0.14$ ) and Cohen’s dz for pairwise comparisons; 95% CIs [10,30].
- **Secondary analyses:** RM-ANOVA for RSA metrics, RPE, Hooper, and VAS with appropriate corrections.
- **Exploratory analyses:** Pearson correlations between PSQI/POMS and outcome variables [23].
- **Missing data and sensitivity:** Pre-specified sensitivity checks reported.
- **Pre-specified subgroups:** None; all participants classified as intermediate chronotype (MEQ) [20,28].

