**Document Date**  
**10 May 2025**

# Strategic Daytime Napping Enhances Agility and Lowers Perceived Exertion but Does Not Improve Fatigue Resistance in Adolescent Soccer Players

## DETAILED TRIAL PROTOCOL

### 1. Structured Abstract

**Background and rationale:** Strategic daytime napping (25 min, 45 min) may acutely influence anaerobic performance in team sports via sleepiness-recovery dynamics.

**Objectives and hypotheses:** Primary objective is to test whether nap conditions improve pro-agility performance. Hypothesis: N25 and/or N45 outperform N0 on pro-agility time. Secondary objectives examine effects on RSA, RPE, Hooper wellness, and VAS alertness/sleep quality. Exploratory objective assesses associations of PSQI and POMS with outcomes.

**Design:** Quasi-experimental, repeated-measures crossover with 3 conditions (N0, N25, N45), 48-h washout, afternoon sessions, testing 60 min post-awakening.

**Participants and setting:** Sixteen competitive male soccer players (U17–U19), isolated dark rooms at  $\approx 22^{\circ}\text{C}$ ; standardized field/lab conditions.

**Interventions:** N0, 25-min, 45-min nap opportunities; sleep–wake verification by Visual Analogue Scale; prohibition of visual/stimulating activities; standardized warm-up monitored by Polar H10.

**Primary/secondary outcomes:** Primary: Pro Agility Test time. Secondary: RSA (6 $\times$ 30 m, 20-s recovery), RPE, Hooper Index, VAS. Exploratory: correlations with PSQI/POMS.

**Sample size:** G\*Power 3.1.9.7 for RM-ANOVA ( $\alpha=0.05$ ,  $1-\beta=0.80$ ,  $f=0.30–0.40$ ) indicated  $\geq 12$ ;  $n=16$  recruited.

**Randomization and blinding:** Within-subject random order of conditions; automated timing to reduce measurement bias; assessor blinding not implemented.

**Statistical analysis (summary):** RM-ANOVA with Bonferroni adjustments; assumption checks (Levene, Mauchly, Greenhouse–Geisser); effect sizes ( $\eta^2$ , Cohen’s  $dz$ , 95% CI); Pearson correlations.

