### 3. Study Design

- **Design:** Quasi-experimental, repeated-measures crossover.
- **Conditions:** N0 (no nap), N25 (25 min), N45 (45 min).
- **Order:** Randomized within participant.
- **Washout:** 48 h between sessions [1].
- **Timing:** Nap starts at 14:00; testing begins 60 min post-awakening [2,3].
- **Testing flow:** Warm-up → Pro Agility → 3-min rest → RSA; RPE after each sprint.

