## 8. Sample Size and Justification

- **Software and model:** G\*Power 3.1.9.7; repeated-measures ANOVA (within-subjects, 3 conditions) [24].
- **Parameters:**  $\alpha=0.05$ ,  $1-\beta=0.80$ ; expected effect size  $f=0.30-0.40$  based on prior literature [9,25,26].
- **Result:** Minimum  $\geq 12$ ; **n=16** recruited to accommodate variability and potential attrition.
- **Note:** Crossover design increases power by using each participant as own control [10].

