## 9. Randomization, Allocation Concealment, and Blinding

- **Randomization:** Within-subject random assignment of condition order.
- **Allocation concealment:** Condition order not disclosed to participants until session day; administered by study staff.
- **Blinding:** Participant blinding is infeasible; automated timing reduces measurement bias; assessor blinding not implemented.
- **Unblinding:** Not applicable.

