## 17. Timeline and Gantt Plan

- **Preparation (Months 0–1):** Ethics approval, device calibration, staff training, pilot tests.
- **Data collection (Months 2–3):** Three sessions per participant, 48-h washout.
- **Analysis (Months 3–4):** Data cleaning, statistical analyses, sensitivity checks.
- **Reporting (Months 4–5):** Manuscript and supplementary materials.

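### The three-session crossover is analysed with condition as the only factor, so a session trend stays in the error term and chance order imbalance goes unadjusted

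*Protocol*

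**What the plan says.** Section 13 states the primary analysis as "RM-ANOVA across N0–N25–N45; Bonferroni where appropriate" and the secondary analyses as "RM-ANOVA for RSA metrics, RPE, Hooper, and VAS with appropriate corrections". The sample-size calculation in section 8 likewise has one within-subject factor, condition, with three levels.

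The design is a crossover. Section 17 gives "Three sessions per participant, 48-h washout". Order is described in section 3 as "Randomized within participant" and in section 9 as "Within-subject random assignment of condition order"; neither says whether the list of orders was balanced.

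No section names session, period or sequence as a model term. Section 13 adds "Pre-specified sensitivity checks reported" without saying what those checks are.

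**The concern.** In a crossover, an outcome can move with session number whatever the condition. That is plausible here. The assessment schedule (section 7.4) and workflow (section 10) show no familiarisation session and no baseline performance test, so the first scheduled agility and sprint tests fall in session 1. Each session includes six 30 m sprints, and players are recruited at the end of the season. RPE, Hooper and VAS are repeated self-reports. The 48-h washout deals with carry-over, not with practice or accumulated fatigue.

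A model with player and condition only handles such a trend poorly in two ways:

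- The trend is counted as residual noise, so a real nap effect is easier to miss.
- If one condition happens to fall later on average than another, part of the trend enters their difference and nothing removes it.

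Balancing the orders cures the second problem but not the first. The trend then cancels from the condition means but remains in the error, and the F test becomes conservative.

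This is not something left open for a separate analysis plan. The protocol states the model, and the stated model lacks a standard crossover term.

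**Working it through.** **Inputs from the protocol.** n = 16; m = 3 conditions; α = 0.05; f = 0.30 to 0.40 (section 8).

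**Inputs assumed, because the protocol gives none.** Within-player correlation ρ = 0.5 (0.3 and 0.7 also tried). A linear session shift of τ within-player SDs per session, with τ = 0, 0.25, 0.35, 0.5 and 1.0.

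**1. The plan's own figure.** λ = f²·N·m/(1−ρ), with degrees of freedom 2 and 2(N−1).

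- f = 0.40, N = 12: λ = 0.16 × 12 × 3 / 0.5 = 11.52 on F(2,22), power 0.816. This reproduces the stated minimum of 12 at the upper end of the f range.
- N = 16: λ = 0.09 × 16 × 3 / 0.5 = 8.64 for f = 0.30 and 0.16 × 16 × 3 / 0.5 = 15.36 for f = 0.40. On F(2,30) the power is 0.706 and 0.926.

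**2. What the trend does to the error term.** Session effects of −τ, 0 and +τ add 2τ² to each player's within-player sum of squares, which has 2 degrees of freedom. With random orders the expected error mean square is therefore multiplied by 1 + τ²: 1.06 at τ = 0.25, 1.25 at 0.5 and 2.00 at 1.0. Simulation gave 1.06, 1.25 and 2.01.

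Dividing λ by 1 + τ² gives a quick check on power without the session term:

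- f = 0.30: 8.64/1.25 = 6.91, power 0.60; 8.64/2 = 4.32, power 0.41.
- f = 0.40: 15.36/1.25 = 12.29, power 0.86; 15.36/2 = 7.68, power 0.65.

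**3. Simulated power, unrestricted random orders.** 20,000 trials per setting, equally spaced condition means, ρ = 0.5; condition-only F(2,30) against session-adjusted F(2,28).

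| τ | f = 0.30, without / with | f = 0.40, without / with |
|---|---|---|
| 0 | 0.71 / 0.68 | 0.93 / 0.91 |
| 0.25 | 0.68 / 0.67 | 0.91 / 0.91 |
| 0.35 | 0.66 / 0.67 | 0.89 / 0.91 |
| 0.5 | 0.60 / 0.67 | 0.86 / 0.90 |
| 1.0 | 0.41 / 0.67 | 0.65 / 0.90 |

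At f = 0.30 and τ = 0.5 the figures are 0.46 / 0.52 for ρ = 0.3 and 0.83 / 0.88 for ρ = 0.7. At τ = 0 they are 0.55 / 0.52 and 0.91 / 0.88.

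**4. Chance imbalance.** For two conditions, the difference in session number within one player has variance 2/3 + 2/3 + 2 × 1/3 = 2. Averaged over 16 players its SD is √(2/16) = 0.354, so the chance shift in a pairwise contrast has SD 0.354τ: 0.09, 0.18 and 0.35 within-player SDs at τ = 0.25, 0.5 and 1.0. A named pair differs by at least 0.5 in mean session number in 18.7% of allocations; at least one of the three pairs does in 39%.

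**5. Type I error without the term.**

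| Orders | τ | Overall | Some pair differs by ≥0.5 | Other allocations |
|---|---|---|---|---|
| Unrestricted | 0.5 | 0.050 | 0.076 | 0.034 |
| Unrestricted | 1.0 | 0.051 | 0.109 | 0.014 |
| Near-balanced | 0.25 | 0.040 | – | – |
| Near-balanced | 0.5 | 0.026 | – | – |
| Near-balanced | 1.0 | 0.004 | – | – |

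With the session term, the error under unrestricted orders is 0.049 to 0.051 in every group. Under near-balanced orders, power with the term is 0.70 (f = 0.30) and 0.92 (f = 0.40) at every shift.

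**The case against.** The planned test is valid on average. Random order prevents systematic bias, overall type I error holds at about 0.05, and with balanced orders the test errs on the cautious side. What remains is efficiency, and that depends on a trend no document quantifies. Below roughly 0.25 to 0.35 SD per session the extra term gains nothing or costs up to about 3 points.

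The larger trends are also large beside the planned effect. With equally spaced means, f = 0.30 implies an N0–N45 difference of 0.735 total SD, or 0.735/√0.5 = 1.04 within-player SD. A shift of 0.5 SD per session moves performance by 1.0 SD from first to last session, about the whole nap effect; 1.0 SD per session is about twice it. The chance shift at τ = 0.5 (SD 0.18) is half the ordinary standard error of a pairwise difference, √(2/16) = 0.35.

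Finally, a random-player mixed model assumes compound symmetry and so drops the planned Greenhouse–Geisser protection; no non-spherical case was simulated.

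All of this stands, and it limits the claim to precision. The 1.0 SD row should be read as an extreme. It does not remove the point: the term costs at most about 3 points if there is no trend and recovers 7 points (f = 0.30) or 4 points (f = 0.40) at 0.5 SD.

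**Conclusion.** The concern holds. The stated primary and secondary models omit session, and nothing else in the protocol supplies it or shows balanced orders. Exact balance over six sequences is impossible with 16 players.

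The consequence is lost precision, plus a shift that depends on the orders actually drawn. It is neither systematic bias nor an inflated average type I error. The size rests on the assumed trend and correlation: negligible up to about 0.25 SD per session, moderate at 0.5 SD, and serious only for a trend that exceeds the planned nap effect. Without the adjustment or a table of order by condition, readers have no means of judging how far a nap-versus-N0 difference reflects session position. The change is worth making because it is cheap, not because the planned test is invalid.

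**What to change.** The right change depends on how far the trial has gone.

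- **Outcome results not yet known.** Analyse primary and secondary outcomes with a linear mixed model (SPSS MIXED): fixed effects for condition and session (1, 2, 3), a random player effect, and Bonferroni-adjusted condition contrasts from that model. Add an unstructured-covariance check, or similar, in place of the Greenhouse–Geisser safeguard.
- **Sessions also not yet run.** Draw orders from a near-balanced list: two full sets of the six sequences plus four distinct orders from a third (12 + 4 = 16). The largest pairwise gap in mean session number is then 3/16 = 0.19. Keep the session term, since balance alone makes the unadjusted test conservative.
- **Results already known.** The title suggests this: "Strategic Daytime Napping Enhances Agility and Lowers Perceived Exertion". Keep the stated RM-ANOVA as primary. Report the session-adjusted model as a labelled sensitivity analysis using the recorded session order, with a table of players per condition per session.

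The cost is wording and, for the adjusted model, two error degrees of freedom (30 to 28). If there is no trend, power falls from 0.709 to 0.676 (f = 0.30) or from 0.926 to 0.905 (f = 0.40) under unrestricted orders, and by less than 1 point under near-balanced orders. No new data are needed beyond the order in which each player's sessions took place.

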## 14. Safety Monitoring and Adverse Event Management

- **Risk profile:** Low-risk procedures involving brief naps and field-based anaerobic tests.
- **Adverse events:** Monitor for syncope, dizziness, musculoskeletal issues; medical evaluation as needed.

- **Reporting:** Serious adverse events reported within 24 h to the ethics committee per institutional policies.

## 15. Ethical Considerations

- **Ethics approval:** Inonu University Non-Interventional Clinical Research Ethics Committee; Approval No: 2024/5635; Date: 05/03/2024.
- **Participant rights:** Voluntary participation, right to withdraw at any time, confidentiality and data protection per applicable law.
- **Conflicts of interest and funding:** The authors declare no conflicts of interest.

## 16. Dissemination and Data Sharing Policy

- **Reporting:** Results will be reported in a peer-reviewed journal with a CONSORT flow diagram will be provided in the final report.
- **Data/code sharing:** De-identified data and analysis code to be shared per journal policies and institutional regulations.

## 17. Timeline and Gantt Plan

- **Preparation (Months 0–1):** Ethics approval, device calibration, staff training, pilot tests.
- **Data collection (Months 2–3):** Three sessions per participant, 48-h washout.
- **Analysis (Months 3–4):** Data cleaning, statistical analyses, sensitivity checks.
- **Reporting (Months 4–5):** Manuscript and supplementary materials.

## 18. Budget and Resources (optional)

- **Equipment:** SECA stadiometer, Toledo scale, Polar H10.
- **Consumables and personnel:** Forms, printing, staff time.

